4.2. INTERIM ANALYSES

Each candidate agent will be evaluated for futility at up to two IAs. For sub-studies under the master protocol, an IA will take place after:

- The appropriate number of primary efficacy endpoint events has occurred (refer to Section 16.5);
- Sponsor authorization of this SAP;
- Sponsor authorization of the analysis sets (refer to Section 5.3);
- Interim or final database lock of each sub-protocol contributing to the shared control group of the candidate agent, as appropriate;
- Interim database lock of the concerned candidate agent (refer to Data Management [DM] Interim Database Lock Plan).

The data cut-off date will be the date when approximately the required number of events is reached for an IA (refer to Section 16.5.1) and the last patient having the event is from the sub-protocol of interest for the IA, because if the last patient with an event is from a sub-protocol other than the one of interest, the patient’s treatment arm will automatically be unblinded since those patients can only be included in the shared placebo plus SoC control arm of the sub-protocol of interest. Efficacy outputs will be based on the full analysis set (FAS; refer to Section 5.1) and

CCI [Redacted]

Master Statistical Analysis Plan

include data from patients who have had the opportunity to complete the Day 29 study visit or discontinued from study before or on the IA data cut-off date, whichever occur first, while safety outputs will be based on the safety analysis set (refer to Section 5.2) and include all data included in the database at the time of the interim database lock.

[figure not shown]
Unless otherwise specified, definitions and derivations for the IAs will be based on those required for the primary analysis contained in this SAP (refers to Section 4.3).

As for the IDMC safety analyses, results of each IA will be reviewed by the IDMC. The IDMC will be asked to make recommendations to the JSC regarding early termination of the evaluation of a candidate agent due to futility based on pre-defined stopping rules (refer to Section 16.5.1).

The JSC will evaluate the IDMC recommendation(s) to make decisions on the candidate agent(s) within the study, and it will provide guidance, advice, and recommendations to the program on relevant clinical issues related to the strategy, implementation, and conduct of the study.

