4.3. PRIMARY ANALYSIS

The primary analysis for a candidate agent will take place after:

- Approximately 350 patients have been randomized to the candidate agent plus SoC active arm of the sub-protocol of interest and approximately 350 patients have been randomized to the shared placebo plus SoC control arm of the sub-protocol of interest (refer to Section 4.5), and last patient randomized into one of these two arms is from the sub-protocol of interest, because if the last randomized patient is from a sub-protocol other than the one of interest, the patient’s treatment arm will automatically be unblinded since those patients can only be included in the shared placebo plus SoC control arm of the sub-protocol of interest;
- The last patient randomized to that candidate agent plus SoC treatment arm or its concurrent shared placebo plus SoC control arm have had the opportunity to complete the Day 29 study visit or discontinued from study before or on the Day 29 study visit;
- Sponsor authorization of this SAP;
- Sponsor authorization of the analysis sets (refer to Section 5.3);
- Interim or final database lock of each sub-protocol contributing to the shared control group of the candidate agent, as applicable;
- Interim database lock of the concerned candidate agent database (refer to DM Interim Database Lock Plan).

The data cut-off date will be the date the last patient completed the Day 29 study visit or discontinued from the study before or on the Day 29 study visit, whichever occurs first.

With the following exception, all planned analyses identified in this SAP will be performed by CCI Biostatistics at the time of the primary analysis of a sub-protocol. The exception is the summary and analysis of the secondary efficacy endpoint incidence of sustained clinical recovery as confirmed by Day 60 (refer to Section 16.2.1.9) which will be performed at the time of the final analysis of a sub-protocol (refer to Section 4.4).

For each sub-protocol, additional outputs to be produced at the time of the primary analysis may be specified in sub-protocol SAPs.

CCI [Redacted]

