- Assuming the all-cause mortality rate through Day 29 is 15% for the concurrent placebo plus SoC arm of a candidate agent, a sample size of 350 patients per arm will provide 80% power to detect an absolute reduction of 6.75% (8.25% rate for the candidate agent plus SoC arm) in the mortality rate by Day 29. Assuming a mortality rate of 15% for the concurrent placebo plus SoC arm of a candidate agent and 19% for the candidate agent plus SoC arm (i.e., an adverse treatment effect of 4%) with a sample size of 350 per arm, the chance to observe a decrease in the mortality rate of at least 1% with a candidate agent plus SoC arm compared to its concurrent placebo plus SoC arm is approximately 4%.

The sample size calculation was performed using EAST 6.5.

CCI

PPD

Version Number: Amendment 1, v1.0
Version Date: 23Apr2021

CCI

For a sub-protocol where the primary analysis population is a subset of the randomized population, the sample size may be adjusted as applicable to power the designated primary analysis population as appropriate.

Each candidate agent may be evaluated for futility at up to two IAs (refer to Section 16.5).

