1. First, the patient’s alive status by Day 29 will be verified as per data collected on the *Death Details* page of the eCRF. If the patient died before or on Day 29, he/she will be censored at Day 29. If the patient has not died by Day 29, then go to step 2;
2. Second, the patient’s study discontinuation status by Day 29 will be verified as per data collected on the *Disposition* page of the eCRF. If the patient discontinued from the study before or on Day 29, he/she will be censored at date of discontinuation from study. If the patient was still ongoing in the study at Day 29, then go to step 3;
3. Last, it will be verified if a patient had a score of 6, 7 or 8 on the 8-point ordinal scale (as captured on the *Ordinal Scale for Clinical Severity* page of the eCRF) before or on Day 29:
 - a. For patients who had a score of 6 on the 8-point ordinal scale and were never discharged from the hospital before Day 29, it will be checked if patient worsened on the 8-point ordinal scale (i.e., had a score < 6) before or on Day 29:
 - i. If so (i.e., patient worsened) and patient never subsequently re-reached a score of 6 before or on Day 29, the patient will be censored at Day 29;
 - ii. If so (i.e., patient worsened) but patient subsequently re-reached a score of 6 before or on

- Day 29, the patient will be considered as having the event and the date of the event will be the earliest date on which the patient re-reached a score of 6;
- iii. If not (i.e., patient did not worsen), the patient will be considered as having the event and the date of the event will be the earliest date on which the patient had a score of 6 before or on Day 29;
- b. For patients who had a score of 7 on the 8-point ordinal scale, it will first be verified if patient was discharged to hospice care as per data captured on the *Hospitalization* page of the eCRF.
 - i. If so (i.e., patient was discharged to hospice care), the patient will be considered as not fit for discharge and will be censored at Day 29;
 - ii. If not (i.e., patient was discharged, but not to hospice care), then go to step c.

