16.2.2. MISSING DATA IMPUTATION METHOD FOR SECONDARY EFFICACY ENDPOINTS

16.2.2.1. Binary Endpoints

For the *incidence of oxygen-free recovery at Day 29* endpoint, the algorithm defined in Section 16.2.1.1 will first be applied. Then, patients with a missing oxygen-free recovery status at Day 29 will be considered as not having met the event for this key secondary efficacy endpoint.

For the *incidence of patients with ≥ 2-point improvement from baseline or fit for discharge on the ordinal scale at Day 29* endpoint (refer to Section 16.2.1.2), patients with a missing ordinal scale score at Day 29 due to patient’s death, discontinuation from study before or on Day 29 or for any other reason (with the following exception) will be considered as not having met the event at Day 29 for that key secondary endpoint. The only exception is for patients with a missing ordinal scale score at Day 29 for which the latest non-missing ordinal scale score before Day 29 was 7 (but not discharge to hospice care) or 8. These patients will be assumed to be fit for discharge at Day 29 and so, as having met the event.

For the *incidence of all-cause mortality through Day 29* endpoint (refer to Section 16.2.1.3), patients with an unknown alive/death status at Day 29 due to discontinuation from study for a reason other than death or missing data will be considered as alive in the analysis, exception of patients for who the last-missing ordinal scale score was 7 and that have been discharged to hospice care before discontinuing from study before Day 29. These patients will be considered as dead at Day 29 for the main analysis of this key secondary efficacy endpoint.

[figure not shown]
For the *clinical recovery by Day 8* endpoint (refer to Section 16.2.1.8), any patient who died before or on Day 8, discontinued from study before or on Day 8 or with missing clinical recovery status at Day 8 will be considered as not having clinical recovery by Day 8. Missing *clinical recovery by Days 15 and 29* will be handled similarly.

For the *sustained clinical recovery as confirmed by Day 60* follow-up endpoint (refer to Section 16.2.1.9), any patient who died before or on Day 60, discontinued study before Day 60 or with a missing 8-point ordinal scale score at Day 60 will be counted as not having sustained clinical recovery.

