16.5. INTERIM ANALYSIS

16.5.1. INTERIM ANALYSIS FOR FUTILITY

Each candidate agent may be evaluated for futility at up to two IAs.

The IAs will be based on analyses of the primary efficacy endpoint (refer to Section 16.1.1), using the analysis methods described in Section 16.1.3.

The IAs are planned at information fractions of approximately 25% and 55% of expected number of confirmed clinical recoveries (refer to Table 1), i.e., after approximately 123 and 270 patients have met the primary endpoint of confirmed clinical recovery on a particular candidate agent plus SoC and its contemporaneous placebo plus SoC, respectively. However, the timing of these IAs may be adjusted due to operational considerations, e.g., actual enrollment rate.

For the IAs, a Pocock beta spending function will be used for non-binding futility boundary specification. This strategy will allow for ineffective agents to be identified early for discontinuation of further evaluation. Assuming no treatment effect for a candidate agent plus SoC arm compared with placebo plus SoC patients included in the control arm of the candidate agent, there is a 49.7% chance that enrolment to this agent is stopped at the first IA and 34.6% chance at the second IA. Under the scenario that treatment has a negative effect on outcome (refer to Table 2), these probabilities become 72.3% and 24.7%, respectively.

The primary analysis for a candidate agent will occur after 350 patients have been randomized to a particular candidate agent plus SoC and have had the opportunity to complete the Day 29 visit, when approximately 490 confirmed clinical recovery events are expected to have been observed in total across the candidate plus SoC arm and placebo plus SoC patients included in the control arm of the candidate agent, unless a candidate agent is stopped early for futility. The final analysis of a candidate agent will occur after all patients randomized to that candidate agent plus SoC and the concurrent placebo plus SoC controls have had the opportunity to complete the Day 60 visit.

Table 1 and Table 2 present a summary of futility incremental probabilities at the first interim and second interim analyses together with Pocock futility boundaries in the scenario of 88.3% estimated power when the IAs occur at information fraction of 25% and 55% of expected number of recoveries, respectively.

CCI

PPD

Version Number: Amendment 1, v1.0
Version Date: 23Apr2021

CCI

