16. EFFICACY ENDPOINTS

Given that only 108 patients were randomized into COV-01-005 sub-protocol by the time enrollment into this sub-protocol was terminated early by the Sponsor and that is expected that less than the third of the total number of patients required by the sample size (i.e., ~700; refer to Master SAP Section 7.1) will be included in the final analysis of this sub-protocol, no statistical inferences will be performed for any efficacy endpoint, but two-sided 95% confidence interval (CI) within each treatment arm will be provided, when possible.

In conformance with the FDA's Guidance for Submission of Abbreviated Report and Synopsis in Support of Marking, summary tables will be presented for the primary and key secondary efficacy endpoints (refer to Master SAP Sections 16.1.1, 16.2.1.1, 16.2.1.2, and 16.2.1.3). Although not required by the previously mentioned FDA's Guidance, summary tables will also be provided for the other secondary efficacy endpoints (refer to Master SAP Sections 16.2.1.4 to 16.2.1.9) in order to be compliant with the publication requirements of *ClinicalTrials.gov*. In addition, summary tables will also be provided for the additional efficacy endpoint of incidence of all-cause mortality through Day 60 (refer to Master SAP Section 16.4.1.1).

[figure not shown]
Efficacy summaries will be performed as described in the Master COV-01 SAP.

CCI

PPD

Version Number: Amendment 2, v1.0
Version Date: 28-Jul-2021

CCI

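### The interim efficacy set admits recently randomized patients only if they died or discontinued, so the hazard ratio used for futility guidance is selected on outcome

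*SAP*

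**What the plan says.** Master SAP Section 4.2 restricts interim efficacy outputs to members of the full analysis set who are "patients who have had the opportunity to complete the Day 29 study visit or discontinued from study before or on the IA data cut-off date", and applies the primary-analysis derivations to the interims.

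Section 16.1.1 classifies each patient in sequence. Step 1: "If the patient died before or on Day 29, he/she will be censored at Day 29". Step 2: "If the patient discontinued from the study before or on Day 29, he/she will be censored at date of discontinuation from study". Only step 3 looks at scores of 6, 7 or 8.

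Section 16.2.2.1 speaks of unknown vital status "due to discontinuation from study for a reason other than death", so death is treated as one reason for discontinuing.

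Sections 16.1.3 and 16.5.1 compare the interim stratified log-rank p-value with non-binding futility limits to guide the IDMC: HR 0.998 (p 0.503) at 123 events and HR 1.121 (p 0.175) at 270.

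For the primary analysis, Section 4.3 waits until the last patients "have had the opportunity to complete the Day 29 study visit or discontinued from study before or on the Day 29 study visit".

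The COV-01-001 and COV-01-005 SAPs (Section 4 of each) drop the interims. The COV-01-004 SAP (Section 3.3) leaves the planned analyses unchanged.

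**The concern.** Take two patients randomized ten days before the cut-off. One has gone home recovered, the other has died. The first is excluded because Day 29 has not been reached. The second is included as a non-event and is kept in the risk set to Day 29, beyond any follow-up possible at the cut-off. A recent patient who drops out also enters as a non-event, even with an earlier score of 6 to 8. Only failures become known early, and the rule collects them without the matching recoveries.

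Similar wording does no harm at the primary analysis, because by then every patient has had the Day 29 opportunity or has discontinued. The problem is specific to the interims.

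What is at stake is a wrong recommendation to stop or continue. If mortality differs between arms, the added non-events push the recovery HR in the direction of that difference. If the agent speeds recovery but mortality is equal, they dilute the HR towards 1.

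**Working it through.** **The plan's own figures.** With z = ln(HR) × √(D/4):
- Look 1: ln(0.998) × √(123/4) = -0.011, one-sided p 0.504 (plan 0.503).
- Look 2: ln(1.121) × √(270/4) = 0.938, one-sided p 0.174 (plan 0.175).
- Power without futility stopping: ln(1.364) × √(490/4) - 1.96 = 1.476, giving 93.0%. With both futility limits applied it is 88.4% (plan 88.3%).
- Futility under HR 1: 0.496 and 0.348 (plan 0.497 and 0.346).

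So the stated p-values are one-sided.

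**Inputs from Master SAP Section 7.1.** Medians 11 and 15 days (HR 1.364); Day 29 mortality 15% on placebo; 8.25% (benefit) or 19% (adverse) on active. Allocation is 1:1 (Section 3.1).

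**Accrual (assumed).** The documents give none for COV-01-004. For COV-01-005, "only 108 patients were randomized into COV-01-005 sub-protocol by the time enrollment into this sub-protocol was terminated early by the Sponsor". From its version 1.0 date (12 October 2020) to termination (7 June 2021) is 238 days, so at least 108/238 = 0.45 per day. The range used is 0.5, 1, 4 and 8 per day into the comparison.

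**How many are added.** With deaths uniform over 28 days, expected recent deaths = rate × 28 × mean mortality × ½. In case (i) below, mean mortality is (8.25% + 15%)/2 = 11.6%, giving 0.8, 1.6, 6.5 and 13.0 deaths beside a look-1 cohort of about 158.

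**Simulation.** 20,000 trials per scenario; exponential recovery; deaths drawn from non-recoverers; cut-off when the 123rd (270th) event patient reaches Day 29; unstratified log-rank test and Cox HR. The shift is the mean HR under Section 4.2 minus the mean HR in the Day-29-opportunity cohort, at look 1, adding deaths only. Its standard error is at most 0.0009. Stopping is shown as cohort → rule.

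| Case | 0.5/day | 1/day | 4/day | 8/day |
|---|---|---|---|---|
| (i) HR 1.364, mortality 8.25% active, 15% placebo: shift | +0.005 | +0.010 | +0.037 | +0.069 |
| Stop by look 2, % | 7.7→7.5 | 7.9→7.4 | 7.7→6.1 | 8.1→4.9 |
| (ii) HR 1.364, 15% in both arms: shift | -0.004 | -0.008 | -0.029 | -0.052 |
| Stop by look 2, % | 7.7→8.0 | 7.9→8.3 | 7.7→9.4 | 8.1→11.2 |
| (iii) HR 1, 19% active, 15% placebo: shift | -0.003 | -0.006 | -0.021 | -0.040 |
| Stop at look 1, % | 49.2→49.8 | 49.9→51.0 | 50.1→54.8 | 50.0→58.8 |

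With HR 1 and equal mortality the shift is within 0.001 of zero. In case (i) the look-2 shifts are about half as large: +0.002, +0.005, +0.017, +0.033.

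**Sensitivity.**
- Case (i) with 5% other discontinuations per arm: +0.004, +0.009, +0.033, +0.061.
- Case (i) at 1, 4 and 8 per day: all deaths in the first 14 days +0.015, +0.052, +0.098; all in the last 14 days +0.005, +0.019, +0.038.
- If deaths are not recorded as discontinuations, at 1, 4 and 8 per day: -0.001, -0.002, -0.005 (5% dropout per arm); -0.003, -0.013, -0.024 (8% active, 4% placebo).

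**Cross-check.** A separately programmed simulation (4,000 trials per scenario, 5% other dropout, 100 patients per 28 days, or 3.6 per day) added no events in any trial. In case (ii) the look-1 HR fell from 1.369 to 1.338. With HR 1 and mortality 15% placebo, 8.25% active, look-1 futility fell from 48.8% to 42.4%.

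**The case against.** **Death is not named in Section 4.2.** Section 16.1.1 reads death and discontinuation from different eCRF pages, Section 16.2.2.1 lists them separately for several endpoints, and Sections 16.1.4 and 16.2.4 impute outcomes for discontinuers in ways that make no sense for known deaths. Counting deaths is therefore an inference from one phrase in Section 16.2.2.1. This stands as a limit. It is not a contradiction, because the 16.1.1 steps are sequential and step 1 has already removed deaths. Without deaths the selection remains, but the shift is much smaller. The clause on whichever comes first that ends the Section 4.2 sentence does not alter who is admitted.

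**The harmful direction is not a plan scenario.** In case (i) the rule stops a beneficial agent less often, and in case (iii) it stops an adverse one more often. Case (ii) is a construction. Non-recovery at 28 days is 2^(-28/15) = 27.4% on control and 0.274^1.364 = 17.1% on active, so 15% mortality means 88% of active non-recoverers die (15/17.1), against 55% on control (15/27.4). This is fair: case (ii) is towards the extreme. But a futility statistic for recovery should not drift with mortality in either direction.

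**Accrual of 4 to 8 per day has no source.** True. The only anchor is a floor, and at 1 per day or less the effect is negligible. Pooling concurrent placebo patients across sub-protocols (Section 4.5) can raise the rate above that of one sub-protocol.

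**The planned test is stratified.** Assume 15% of patients at severity 2, control recovery 30% in that stratum and 80% elsewhere, and threefold average mortality in it. The stratified case (i) shift at 1, 4 and 8 per day was then +0.008, +0.030, +0.052, against +0.010, +0.040, +0.072 unstratified. Case (iii) fell by about 10 to 20%; case (ii) did not shrink.

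**Consequence.** The boundary is non-binding guidance, the steering committee decides, type I error is not inflated, and the IDMC charter is not among the documents. All of this limits the harm without justifying the rule.

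**Conclusion.** The concern holds. As written, Section 4.2 with steps 1 and 2 of Section 16.1.1 adds recent patients to the interim efficacy set only when they are non-events. The mean look-1 HR shift is about 0.01 or smaller at up to 1 patient per day. At 4 to 8 per day it is roughly 0.02 to 0.07 in absolute size, with its sign set by mortality and recovery, and it is about half that at look 2. These sizes assume that death counts as discontinuation, deaths are uniform over 28 days, recovery is exponential, and accrual is as stated. If only other dropouts enter, the shift is at most 0.024 in the cases tried. The practical consequence is confined to futility guidance for COV-01-004 and any later agent under the master plan.

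A minor point: the p-value columns in the futility tables show neither side nor inequality, while Section 16.1.3 sends to them the p-value judged at two-sided 0.05.

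**What to change.** Replace the inclusion rule in Master SAP Section 4.2 with wording such as: *Interim efficacy outputs include every patient in the full analysis set randomized early enough to have had the Day 29 opportunity by the cut-off, whatever the outcome. Later patients, including those who have died or discontinued, are not included; they remain in the safety outputs.* This works under either reading of discontinuation.

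The cost is one sentence. The event count and interim timing do not change, because only non-events are removed. In case (i) look 1 loses on average 0.8, 1.6, 6.5 or 13.0 recent deaths at 0.5, 1, 4 or 8 per day. With 5% other discontinuations it loses 1.1, 2.2, 9.0 or 17.9 patients beside a cohort of about 167.

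For the minor point, head the p-value column in SAP Tables 1 and 2 and Protocol Tables 6 and 7 as one-sided for HR above 1, with futility at or above the value, at planned timing. State that the p-value and HR limits are both re-derived from the Pocock beta-spending function at the actual event counts. Because "the timing of these IAs may be adjusted due to operational considerations", 0.503 and 0.175 should not be fixed. The function 0.117 × ln(1 + (e - 1)t), which reproduces both, gives p 0.611 at 98 events and 0.412 at 147 for the first look.
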